12.2. Study Drug Packaging and Labeling

ALXN1210 will be supplied in a one-vial-per-kit configuration. Each vial and carton will be labeled according to local regulatory requirements.

12.3. Study Drug Storage

ALXN1210 vials must be stored in refrigerated conditions at 2°C to 8°C (36°F to 46°F) and protected from light. ALXN1210 vials should not be frozen or shaken.

12.4. Study Drug Preparation

Preparation of ALXN1210 and placebo SC doses must be performed in accordance with study center-specific local standards by qualified and study-trained pharmacy personnel.

The handling and preparation of materials used to prepare and administer the investigational product must be carried out using aseptic techniques for sterile products. For each subject, doses will be prepared as required for the dose cohort.

12.4.1. Preparation of ALXN1210 SC and Placebo SC

ALXN1210 SC and placebo SC will be prepared in a blinded fashion in a syringe for SC administration. There will be no dilution of ALXN1210 SC or placebo SC. ALXN1210 SC and placebo SC will be placed directly into the syringe.

The pharmacy staff preparing the SC injections for Cohort 1a and Cohort 1b will be unblinded, as will the study drug administrator(s). All other staff involved will be blinded (Section 11.7).

Please refer to the pharmacy manual for additional dose preparation instructions and the SOM for additional information regarding blinding and study drug administration.

12.4.2. Preparation of ALXN1210 IV

ALXN1210 IV is designed for infusion by diluting into commercially available saline (0.9% sodium chloride injection; Ph Eur or BP) for IV infusion at a maximum rate of 333 mL/hr, excluding interruption for safety or technical reasons.

The pharmacy staff preparing the infusions for Cohort 2 will be unblinded to study drug assignment; the subjects and all other study center staff involved in the study will also be unblinded (Section 11.7).

Please refer to the pharmacy manual for additional dose preparation instructions.

12.4.3. In-Use Shelf Life

ALXN1210 IV will be diluted with 0.9% sodium chloride injection, Ph Eur or BP, before administration (dosing solution). The in-use shelf life of the dosing solution is 4 hours at room temperature 15°C to 25°C (59°F to 77°F). The expiration date and time of the dosing solution is calculated from breach of the first vial. The dose must be administered within the expiration date and time.

Each 1-mL syringe of ALXN1210 SC or placebo SC that is drawn up (4 syringes per subject) should be administered within 1 hour once drawn up from vial to syringe.

12.5. Administration

12.5.1. Administration of ALXN1210 SC and Placebo SC

All doses of ALXN1210 SC or placebo SC will be administered by four 100-mg SC injections of 1 mL each (Table 7) in the abdominal area. All four 1-mL injections should be administered over a 15-minute period, and there should be at least 15 minutes between the end of injection in one subject and the start of injection in the next subject.

Cohort	Study drug and dose	Number of 1-mL syringes prepared	Total volume administered
1a	1 dose of 400 mg ALXN1210 SC or placebo SC	4	4 mL
1b	1 dose of 400 mg ALXN1210 SC or placebo SC	4	4 mL

Table 7: Dosing Reference Chart for ALXN1210 SC and Placebo SC Preparation

For further information regarding the preparation and administration of study drug, please see the pharmacy manual. Please refer to the SOM for additional information regarding blinding and study drug administration.

12.5.2. Administration of ALXN1210 IV

All doses of ALXN1210 IV will be administered by IV infusion, using IV sets with in-line filters, at a maximum rate of 333 mL/hr, excluding interruption for safety or technical reason. There should be at least 15 minutes between the end of infusion in one subject and the start of infusion in the next subject. For further information regarding the preparation and administration of study drug, please see the pharmacy manual.

Table 8:	Dosing Reference	Chart for ALXN1210 IV	⁷ Preparation
----------	-------------------------	-----------------------	--------------------------

Cohort	Study drug and dose	ALXN1210 volume per dose (mL)	Diluent volume per dose (mL)	Infusion volume (mL)	Maximum infusion rate (mL/h)	Minimum infusion duration ¹ minutes (hour)
2	1 dose of 400 mg ALXN1210 IV	40	40	80	333	15 (0.25)

¹ Infusion duration is approximate.

Please refer to the pharmacy manual for additional dose preparation instructions.

12.6. Management of Potential Adverse Events During Study Drug Administration

Some subjects treated with IV infusions of mAbs have experienced concurrent infusion-related reactions with signs or symptoms that can be classified as acute allergic reactions/ hypersensitivity reactions or cytokine release syndrome.

Subjects will be closely monitored during and after study drug administration for any symptoms of anaphylaxis and other hypersensitivity reactions, including circulatory and/or respiratory changes or arrest, or urticaria, arthralgias, myalgias, or other signs of related reactions. Adequate treatment will be immediately available. Infusion-associated AEs may occur, and depending on their type and severity, discontinuation of infusion may be required. Subjects will be informed of early symptoms and signs of hypersensitivity reactions including hives, swollen face, eyelids, lips, or tongue, or trouble with breathing. An acute infusion-reaction algorithm will be used to manage infusion-related reactions (see Appendix 1: Acute Infusion Ste reactions Algorithm). In this study, regular assessments to monitor infusion reactions and infusion site reactions will be done. To ensure that reactions can be dealt with promptly, there will be at least 15 minutes between the end of infusion/injection in one subject and the start of infusion/injection in the next subject. No

more than 6 subjects will be dosed per day. Any reactions will be treated and taken into account in the dose continuation/escalation and toxicity rules (see Table 3). If anaphylactic reactions occur, the current "UK Treatment Guideline for Anaphylactic Reactions" of the UK Resuscitation Council will be followed (see Appendix 2: United Kingdom Resuscitation Council Anaphylaxis Algorithm).

Subjects who experience a severe reaction during administration of study drug that results in discontinuation of study drug should undergo all scheduled safety, immunogenicity, PK, and PD evaluations required by the protocol. Subjects will therefore be instructed to attend all scheduled visits and undergo all procedures per protocol.

Similar reactions could potentially occur with SC injections of mAbs.

12.7. Study Drug Accountability

The study center must maintain accurate records demonstrating dates and amount of study drug received from Alexion, to whom study drug was dispensed (a subject-by-subject accounting), and accounts of any study drug accidentally or deliberately destroyed.

Unless otherwise notified, all vials, both used and unused, must be saved for study drug accountability. At the end of the study, a final reconciliation must be made between the amount of study drug supplied, dispensed, and subsequently destroyed or returned to Alexion.

A written explanation will be provided for any discrepancies. After reconciliation, the investigator must destroy or return to Alexion all unused vials of study drug as instructed by Alexion.

12.8. Study Drug Handling and Disposal

If any study drug supplies are to be destroyed at the study center, the investigator must obtain prior approval by Alexion. The investigator must notify Alexion, in writing, of the method, date, and location of the destruction.

At the completion of the study, in order to satisfy regulatory requirements regarding drug accountability, all remaining investigational product inventory will be reconciled and retained or destroyed according to applicable United Kingdom regulations and the policies and procedures applicable to the study center.

For handling instructions, please refer to the pharmacy manual.

13. PHARMACOKINETIC AND PHARMACODYNAMIC ASSESSMENTS

13.1. Serum Sample Collection

The total anticipated volume of serum collected per subject for clinical laboratory, PK, PD, and immunogenicity assessments will not exceed 500 mL per subject. Please refer to the laboratory manual for specific details regarding serum volumes.

After study drug administration, serum samples for the determination of serum ALXN1210 concentrations and for analyses of total and free C5 concentrations, cRBC hemolysis, and potentially other measures of C5 activation will be collected at the following time points, with the actual serum sampling dates and times being recorded and used in the PK and PD calculations:

Serum concentrations of ALXN1210 will be assayed from the following sampling time points: pre-dose (within 15 minutes prior to start-of-infusion/injection [SOI]); Day 1 at end of infusion/injection (EOI), 30 minutes post EOI, and the following time points following SOI: 2 h, 4 h, and 8 h; Day 2 (24 h); Day 3 (48 h); Day 5 (96 h); Day 8 (168 h); Day 15 (336 h); Day 22 (504 h); Day 29 (672 h); Day 36 (840 h); Day 43 (1008 h); Day 50 (1176 h); Day 57 (1344 h); Day 71 (1680 h); Day 90 (2136 h); Day 120 (2856 h); Day 150 (3576 h); and Day 200 (4776 h).

Please refer to the SOM for the time windows for collection, and to the laboratory manual for details on sample collection, including the serum volume requirements.

13.2. Criteria for Evaluation

All subjects providing an adequate number of serum PK samples to characterize a concentration-time profile will be included in the PK analysis population. All subjects providing PD samples will be included in the PD analysis population.

13.3. Sample Analysis

Detailed instructions on the procedure for collection, processing, storage, and shipment of the serum samples for PK and PD analyses will be provided in the laboratory manual. All sample analyses will be performed by Alexion or designee.

14. IMMUNOGENICITY ASSESSMENTS

14.1. Serum Sample Collection

Serum samples will be collected at the following time points: pre-dose (within 15 minutes prior to SOI), and on Days 15 (336 h), 29 (672 h), 57 (1344 h), 90 (2136 h), 120 (2856 h), 150 (3576 h), and 200 (4776 h) and analyzed for ADA to ALXN1210.

Further characterization of antibody response may be conducted as appropriate based on PK/PD and safety data of ALXN1210.

Please refer to the SOM for the time windows for collection, and to the laboratory manual for details on sample collection, including the serum volume requirements.

14.2. Criteria for Evaluation

All subjects who provide a pre-dose and a post-dose sample for ADA will be included in the immunogenicity analysis population.

14.3. Sample Analysis

The immunogenicity assay will evaluate ADA to ALXN1210. Detailed instructions on the procedure for collecting, processing, storing, and shipping serum samples for immunogenicity analysis will be provided in the laboratory manual. All sample analyses will be performed by Alexion or designee.

15. ASSESSMENT OF SAFETY

Safety assessments will include TB testing, physical examination findings, vital sign measurements, immunogenicity (ADA) testing, laboratory evaluations, ECGs, infusion site and injection site evaluations (eg, bleeding, bruising, erythema, swelling, induration, and pain), and monitoring of AEs. Adverse events will be graded according to the National Cancer Institute Common Terminology Criteria for Adverse Events v4.03 (CTCAE v4.03), published 14 Jun 2010. Laboratory evaluations will include hematology, chemistry, and coagulation panels; CBC with differential; urinalysis; and serum pregnancy test for female subjects.

15.1. Safety Parameters

Clinical and laboratory assessments will be performed to assess safety of ALXN1210. The timing of the assessments is described in the Schedule of Assessments (Section 9). Abnormal results should be followed until resolution or stabilization.

15.1.1. Demographic/Medical History

A review of demographic parameters, including age, gender, race, and ethnicity will be performed as described in the Schedule of Assessments (Section 9). A complete medical history will be taken and documented in the eCRF.

15.1.2. Vital Sign Measurements

Vital sign measurements will be taken after the subject has been resting in the supine or semirecumbent position for at least 5 minutes and will include temperature (°C; oral), respiratory rate, supine blood pressure, and pulse. The timing of vital sign measurements is described in the Schedule of Assessments (Section 9). Out-of-range blood pressure or pulse measurements will be repeated at the investigator's discretion. Any confirmed, clinically significant vital sign measurements will be recorded as AEs.

15.1.3. Weight, Height, and BMI

Weight, height, and BMI will be recorded as described in the Schedule of Assessments (Section 9).

15.1.4. Physical Examination

Each examination will include the following assessments: general appearance; skin; head, ears, eyes, nose, and throat; neck; lymph nodes; chest; heart; abdominal cavity; limbs; central nervous system; and musculoskeletal system.

15.1.5. Electrocardiogram

A triplicate 12-lead ECG will be obtained after the subject has been resting for at least 5 minutes. The timing of ECGs is described in the Schedule of Assessments (Section 9). In addition, continuous cardiac registration will be performed at each dose administration from pre-dose to end of IV infusion in Cohort 2 and from pre-dose to 3 hours post end of SC injection in Cohorts 1a and 1b.

Heart rate, PR, QRS, RR, and QT will be measured and corrected QTcF intervals will be calculated.

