¹ Permissible windows for study assessments are described in the study operations manual. ² EOI will be approximately 15 minutes after SOI.

³ Subject will be discharged from CRU after completing all Day 5 assessments. Subjects will be provided a "Study Participant ID card" with information for Healthcare Provider and participant on symptoms of meningitis infection.

⁴ Signed and dated EC-approved ICF must be obtained before any study-specific screening procedures are performed.

⁵ For subjects who do not have adequate documentation of prior MCV4 immunization or serogroup B vaccination, MCV4 immunization will be performed at least 56 days prior to first dose on Day 1, and vaccination for serogroup B meningococcal infections will be administered at least 56 days prior to Day 1 dosing with a booster administered at least 28 days prior to dosing on Day 1.

⁶ Complement activity, confirmed by a suitable assay such as complement alternative pathway (CAP) ELISA/C5 (hemolysis) inhibition, will be performed at screening to confirm subjects do not have a complement deficiency.

⁷ The sample drawn on Day -1 will be stored for future analysis should the post-dose sample indicate that complement has not normalized.

⁸ Serum pregnancy test for all female subjects to confirm a female subject is not pregnant.

⁹ On Dav 1, vital sign measurements will be assessed pre-dose (within 15 minutes prior to SOI) and at EOI, 30 minutes after EOI, 2 hours after SOI, 4 hours after SOI, and 8 hours after SOI.

¹⁰On Day 1, triplicate 12-lead ECGs will be performed pre-dose and approximately 15 minutes post-EOI.

¹¹Continuous cardiac registration predose through duration of IV infusion (Cohort 2) and until 3 hours post SC injection (Cohorts 1a and 1b).

¹²Infusion or injection site evaluations will be done within 15 minutes of the start of infusion/injection and \pm 15 minutes of the other scheduled times on Day 1. Indurations or reactions < 1cm will not be listed as an adverse event unless it persists for more than 24 hr. Pain at site of infusion or injection will be assessed using a Visual Analog Scale (0-10). Pain will not be assessed pre-dose.

¹³The investigator or designee will meet with the subject at each visit to discuss the potential safety risks of ALXN1210, and to address any safety concerns on the part of the subject.

¹⁴Collection of AEs and SAEs will begin at ICF signing.

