16. ADVERSE EVENT MANAGEMENT

The investigator is responsible for detecting, assessing, documenting, and reporting all AEs. All AEs will be recorded from the signing of ICF until study completion. There is no time limit for SAEs that are considered causally related.

All observed or volunteered AEs, regardless of causal relationship, must be reported and recorded in the data capture system. Adverse events reported by the subject and/or parent or legal guardian, and/or identified in response to an open-ended question from study personnel, or revealed by observation, physical examination, or other study procedures must be collected and recorded.

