4.4. Safety Analysis

Safety analyses will be performed on the safety population, and will be reported by each treatment group and overall. Safety analyses will include an analysis of all

Statistical Analysis Plan

AEs, ECGs, clinical laboratory data, vital sign measurements, and physical examination results and will be presented using descriptive statistics. No inferential statistical analyses are planned on the safety parameters of this study.

Adverse Events

The incidence of treatment-emergent (after dosing) AEs (TEAEs) will be summarized using the safety population. The Medical Dictionary for Regulatory Activities (MedDRA) dictionary Version 19.0 (or higher) will be used to classify all AEs reported during the study by System Organ Class (SOC) and Preferred Term. A summary of TEAEs including the incidence of subjects who experienced TEAEs (number and percentage of subjects) and incidence of TEAEs (number of events) will be presented for each treatment group and overall, by severity and by relationship to study drug. TEAEs and serious TEAEs will be summarized by SOC and Preferred Term for each treatment group and overall, by severity, and by relationship to study drug. Treatment group will be categorized by the treatment that was actually received at the date of AE onset (i.e., ALXN1210 SC, ALXN1210 IV or ALXN1210 placebo SC). Subjects having multiple AEs within a category (e.g., overall, SOC and Preferred Term) will be counted once in that category. For severity tables, a subject's most severe event within a category will be counted. For relationship tables, a subject's event with greatest relationship to study drug within a category will be counted. In each table, SOC and Preferred Term will be presented in descending order of overall incidence rate (alphabetical order will be used in case of equal rates). All TEAEs, serious TEAEs, TEAEs resulting in withdrawal from the study, TEAEs occuring during study drug administration and AEs that occurred before first dose administration will be presented in by-subject listings.

Medical History

Medical history data will be coded using MedDRA dictionary Version 19.0 (or higher) and listed individually.

Vaccination Status

A listing of MCV4 and Serogroup B vaccination status and dates will be presented individually.

Study Drug Administration

Study drug administration data will be listed individually.

Vital Signs

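### From the start of dosing, continuous cardiac monitoring lasts about 12 to 13 times longer in the SC cohorts than in the IV cohort, and the SAP's SC-versus-IV tables of cardiac adverse events take no account of it

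*Protocol*

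**What the plan says.** - **Monitoring windows.** Protocol 15.1.5 sets the span of continuous cardiac registration as "pre-dose to end of IV infusion in Cohort 2 and from pre-dose to 3 hours post end of SC injection", the second window being that of the SC cohorts (1a and 1b). Table 4, footnote 11 gives the same split, except that it counts the 3 hours from the SC injection without saying from its end. Neither document gives a reason for the difference.
- **Length of dosing.** Table 4, footnote 2 says "EOI will be approximately 15 minutes after SOI" (SOI and EOI are the start and end of infusion or injection). Protocol 12.5.2 gives the infusion "at a maximum rate of 333 mL/hr", and Table 8 lists 80 mL and a minimum duration of 15 minutes, marked approximate. For SC dosing, Protocol 12.5.1 says "All four 1-mL injections should be administered over a 15-minute period".
- **What becomes an adverse event.** Protocol 16 requires that adverse events "revealed by observation, physical examination, or other study procedures must be collected and recorded". Protocol 16.1 sets the threshold for an abnormal test finding: for example, it comes with a symptom, needs further diagnostic work-up or intervention, or is judged clinically significant.
- **Analysis.** The first primary objective sets the safety of SC against IV (Protocol 6.1, SAP 2.1). SAP 4.4 says "TEAEs and serious TEAEs will be summarized by SOC and Preferred Term for each treatment group and overall, by severity, and by relationship". It counts events after dosing as treatment-emergent (TEAEs). It does not mention the continuous registration, how an event was detected, or unequal observation time.

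**The concern.** A comparison of event incidence between groups assumes that events are looked for equally hard in each. Here one detection procedure stops when the infusion ends in the IV cohort and continues for 3 more hours in the SC cohorts. If rhythm or rate events occurred equally often by either route, the monitor would still find more of them after SC dosing.

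The direction is predictable: an apparent SC excess in cardiac TEAEs. With 24 subjects on active SC and 12 on IV, one or two extra events would show in a descriptive table, and a reader of that table could not tell a route effect from a longer look.

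**Working it through.** **Infusion time.** Table 8: volume / maximum rate = 80 / 333 h × 60 = 14.4 min. This reproduces the stated approximate 15 min.

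**Monitored time from the start of dosing.** Pre-dose time is left out because pre-dose findings are not treatment-emergent.

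- SC: 15 min of injections + 180 min = 195 min (3.25 h)
- IV: 15 min (0.25 h)
- Ratio: 195 / 15 = 13.0
- After dosing ends: 180 min against 0 min

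**Sensitivity of the ratio**

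| Variation | Ratio |
|---|---|
| Unrounded infusion of 14.4 min | 195 / 14.4 = 13.5 |
| 3 hours counted from start of injection | 180 / 15 = 12.0 |
| Infusion takes 30 min (assumed) | 195 / 30 = 6.5 |
| Infusion takes 60 min (assumed) | 195 / 60 = 3.25 |

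Even if pre-dose monitoring were counted, an assumed common segment of 15, 30 or 60 min gives 210 / 30 = 7.0, 225 / 45 = 5.0 or 255 / 75 = 3.4.

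In total, planned monitored time is 24 × 3.25 = 78 subject-hours on active SC and 12 × 0.25 = 3 on IV. That 26-fold contrast includes the 2:1 group sizes, which do not affect incidence. The per-subject ratio is the relevant one.

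**What this could do to incidence.** The documents give no rate for monitor-detected adverse events. The rates below are assumptions, the same for both routes, and only illustrate the mechanism. Probability of at least one event = 1 − exp(−rate × hours).

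| Assumed rate per hour | SC (3.25 h) | IV (0.25 h) | Expected SC subjects of 24 | Expected IV subjects of 12 |
|---|---|---|---|---|
| 0.01 | 3.2% | 0.25% | 0.77 | 0.03 |
| 0.02 | 6.3% | 0.5% | 1.5 | 0.06 |
| 0.05 | 15.0% | 1.2% | 3.6 | 0.15 |

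If the true rate is well below 0.01 per hour, the expected difference is a small fraction of one subject.

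**What is equal across cohorts.** In Tables 4 and 5 the following share one timetable:

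- 12-lead ECGs, including triplicates pre-dose and about 15 min after EOI
- vital signs at EOI, 30 min after EOI, and 2, 4 and 8 h after SOI
- residence in the unit to Day 5
- continuous event collection

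SC placebo has the same monitoring window as SC active.

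**The case against.** The case for leaving the plan alone has real weight.

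- **Not every monitor finding is an adverse event.** A reader might infer from Protocol 16 that anything on the trace must be recorded as one. The sentence concerns adverse events revealed by procedures, and Protocol 16.1 sets the threshold. This stands and narrows the point. It does not remove it, because an asymptomatic finding can still qualify through clinical significance or further work-up.
- **The IV cohort is not unmonitored after its infusion.** A reader might infer that it is. The scheduled ECG, vital signs and residence in the unit say otherwise. Only the continuous registration stops.
- **The effect on overall incidence is probably small.** Events are collected over 200 days, and 3 hours is 3 / 4776 = 0.06% of the time to the last visit. The safety analysis is descriptive, so no error rate is at stake. This stands for the any-TEAE row. It carries less weight for a cardiac row, where few events are expected.
- **The SAP already lists TEAEs that occur during study drug administration.** That listing covers roughly the common window. It does not say how an event was detected and does not alter the summary tables.
- **Longer observation of the newer route may be deliberate.** The 400 mg IV dose had already been given to healthy subjects (Protocol 5.1.1), and Cohort 1a exists to look at the SC formulation first (Protocol 8.5). This is plausible, but it is not given as the reason. A good reason for the difference would also not make the counts comparable.
- **Cutting the main comparison off at EOI would lose information.** This is right. It would leave 15 minutes of monitoring per subject, or 6 subject-hours on SC and 3 on IV. Such a display should be supportive only.

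**Conclusion.** The point holds as a limited ascertainment difference and is a low-cost improvement. From the start of dosing the continuous monitor runs about 195 minutes on SC and 15 minutes on IV, about 12- to 13-fold. This rests on the documents' approximate minimum infusion time and falls with a slower or interrupted infusion.

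The consequence is confined mainly to cardiac TEAEs that only the monitor would reveal and that meet the Protocol 16.1 criteria, in the SC-versus-IV comparison. SC active against SC placebo is not affected.

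A reader might go further and infer that overall TEAE incidence is materially biased against SC. The documents do not support that: it would need a rate of monitor-detected events, which they do not give, and all other ascertainment is the same. Nor do Protocol 15.1.5 and footnote 11 contradict each other on the split by route. They differ only on whether the SC clock starts at the end of injection.

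**What to change.** 1. **SAP 4.4.** Keep all TEAEs in the main tables. Flag those identified only by continuous cardiac registration.
2. **SAP 4.4.** Add one supportive SC-versus-IV display of cardiac TEAEs. Count monitor-only events in the window common to all cohorts (start of dosing to EOI), show later SC monitor-only events on a separate line, and footnote the unequal windows.
3. **Protocol 15.1.5 and Table 4, footnote 11.** The sponsor and investigator should state why the windows differ, and use the same wording for when the 3 hours start. No monitoring duration is proposed here.

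The cost is one detection-method flag and one extra table. The documents show no such data field, so each cardiac TEAE in the monitored period would need a short judgement on how it was found. Because the IV cohort is open-label, the rule for that judgement should be written down beforehand and applied no later than the Blind Data Review Meeting. The common-window display will rest on about 15 minutes per subject and should be described as supportive. No event leaves the main tables, and the SAP part of the change does not affect subject care.
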